### 6. Study Purposes and Objectives:

**Hypothesis:** Snellen uncorrected distance visual acuity will be the same with wavefront optimized LASIK/PRK treatment compared to topography guided custom ablation LASIK/PRK treatment.

**Objectives:** We aim to conduct a prospective trial comparing the post-operative outcomes in fellow eyes, one of which has undergone wavefront optimized LASIK or PRK treatment and one of which has undergone topography guided LASIK or PRK in order to determine whether equivalent patient visual outcomes are achievable at our institution using both forms of LASIK or PRK treatment.

The outcomes we will measure include uncorrected visual acuity.

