### 6. Describe all the procedures chronologically, from screening/enrollment through study closeout, which will be completed in the research project.

Patients who are interested and eligible to participate in the study will be enrolled and will read and sign the study informed consent prior to surgery.

Participants will have an in depth discussion with our refractive surgery coordinator regarding refractive surgery. Patients will choose LASIK/PRK surgery based on our standard pre-operative discussion that is provided to all patients. As is standard for laser refractive

candidates, the advantages and disadvantages of LASIK/PRK compared to the other refractive surgical options will be discussed.

Following patient selection of their preferred type of refractive procedure they will be randomized as discussed below, and only patients who elect for LASIK/PRK will be included in our study.

Prior to surgery, one eye from each patient will be randomly assigned to receive either Wavefront optimized or Topography Guided treatment. Each patient in the study will have a fellow eye enrolled in the other treatment group. Patients will either receive LASIK treatment or PRK treatment in both eyes but the eyes will be randomized to topography guided or wavefront optimized forms of treatment.

All surgical procedures will be performed according to the standard of care and the surgeons' standard practices. The study outcome measures are standard of care for pre-operative and post-operative evaluation of refractive surgery patients.

The primary outcome measures will be visual acuity at the pre-operative and post-operative and post-operative time points.

Study outcome measures will be evaluated for each treated eye of each subject at each study time point. Additional examinations between study time points may be performed as necessary according to the surgeon's usual care, but will not be considered part of the study data. Patients have a right to withdraw at any time and future medical care will not be influenced by their lack of participation.

If enhancement surgery is deemed necessary and performed during the one-year post-operative period, study data collection will end for that eye at the time of the enhancement. All prior collected data will be included in the statistical analysis.

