**Eyes will be evaluated with the following standard of care procedures:**

- pupil size measured in mesopic format: pre-operative only
- corneal pachymetry: pre-operative only
- uncorrected visual acuity: pre-operatively and post-operative Day 1 (+1 day), Week 1 (+/- 3 days), Month 1 (+/- 10 days), Month 3 (+/- 1 month), Month 6 (+/- 1 month) and Month 12 (+/- 1 month).
- best corrected visual acuity and manifest refraction: pre-operatively and post-operative Month 1 (+/- 10 days), Month 3 (+/- 1 month), Month 6 (+/- 1 month) and Month 12 (+/- 1 month)

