**7. Are all procedures for research purposes only (non-standard or non-standard of care procedures)?**

Yes  No

**If no, list the procedures that are performed for research purposes only (non-standard or non-standard of care procedures):**

All procedures are considered within the standard of care for laser refractive surgery and will be billed to patients in the usual manner; however, participants will be eligible for a reduced study fee for their surgery and post-operative care. Laser refractive surgery is considered cosmetic surgery and is never billed to insurance. The refractive surgery charge includes standard post-operative examinations up to one year.

If enhancement surgery is deemed necessary during the one-year post-operative period, this will be included based on the patient's initial fee, as is standard of care. Any other costs related to the management of adverse events, or if additional refraction correction is necessary at some time after the one-year postoperative period, will remain the patient's responsibility and are not included in the study surgery fee.

Randomization, data collection and analysis are being done for research purposes only.

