**8. Is there a safety monitoring plan for this study?**

Yes  No

**9. Provide a summary of the statistical methods, data analysis, or data interpretation planned for this study. Factors for determining the proposed sample size (e.g., power) should be stated.**

Standard statistics will be calculated and used to describe the two treatment groups in terms of all study variables. Statistics will be compiled for each variable at the study time points listed in the data collection protocol. Patients withdrawn from the study prior to surgery will not be included in the data analysis and will be replaced in the enrollment group. For eyes that require enhancement surgery, only data collected prior to the enhancement surgery will be included in the statistical analysis.

Power calculations for this study are based on similar prospective, randomized contralateral eye laser refractive studies comparing wavefront optimized and wavefront guided treatments. Previously published contralateral eye studies demonstrated statistically significant results for similar endpoints as our study by including in the range of 70-100 patients for each treatment group. To ensure sufficient patient numbers accounting for 20-30% drop out, including patients that may need enhancement surgery and may not be able to complete the study.

References:

PI: [name]

Submitted: 10/25/2016

**Title:** Outcomes of topography-guided laser-assisted in situ keratomileusis (LASIK) and phororefractive keratectomy (PRK) compared to wavefront optimized LASIK and PRK

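### Enhancement ends an eye's data and is never compared between treatments, so later-visit acuity summaries cover only eyes not retreated and can understate a true difference

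*Combined protocol and SAP*

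**What the plan says.** Two places set the same rule. Study Information, item 6 (procedures) says that after an enhancement in the first year "study data collection will end for that eye at the time of the enhancement", and adds: "All prior collected data will be included in the statistical analysis". Item 9 (statistical methods) repeats it: "For eyes that require enhancement surgery, only data collected prior to the enhancement surgery will be included in the statistical analysis".

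Item 9 describes the analysis itself only in general terms: "Statistics will be compiled for each variable at the study time points listed in the data collection protocol". For uncorrected acuity those time points run from Day 1 to Month 12 (item 6, list of evaluations). No test, model or primary visit is named.

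Enhancement appears in two other places. It is part of the enrolment allowance, "accounting for 20-30% drop out, including patients that may need enhancement surgery and may not be able to complete the study", and it is a fee item in item 7: "If enhancement surgery is deemed necessary during the one-year post-operative period, this will be included" under the initial fee. It is not among the outcomes. Study Purposes and Objectives says only: "The outcomes we will measure include uncorrected visual acuity". Item 6 names visual acuity as primary, and its list of evaluations does not mention enhancement. The plan has no between-treatment comparison of enhancement and no rule for the fellow eye of an enhanced eye.

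**The concern.** Each patient has one eye in each treatment, so the comparison is within patients. An eye is enhanced after it has received its randomised treatment, and a disappointing result of that treatment is a natural reason for it. If enhanced eyes leave the later summaries, those summaries are selected on a consequence of treatment. The treatment that leaves more eyes with poor acuity loses more of its poor eyes, and the two groups look more alike at later visits than they are.

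The trial asks whether the two treatments give equal uncorrected acuity, so a bias toward no difference runs in the direction of its hypothesis. No primary visit is fixed, so an affected visit may carry the conclusion.

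The need for retreatment is also a randomised comparison in its own right, and the plan leaves it unreported.

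**Working it through.** **Documents.** Items 6 and 9 agree that an enhanced eye contributes nothing after enhancement. Taken with by-visit summaries, a Month 12 summary contains only eyes not retreated by Month 12. Collection stops for the enhanced eye alone, so its fellow remains without a partner. The plan gives no figure on this point to reproduce.

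**Illustrative inputs (all assumed).** Acuity in logMAR (higher is worse), normal, better-arm mean 0, other arm 0.050, fellow-eye correlation 0.5. In both arms an eye worse than 0.20 is enhanced with probability p. Mild case: SD 0.10, p = 0.3. Heavy case: SD 0.15, p = 0.8.

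**Enhancement rate** = p × Q(z), where z = (0.20 − mean)/SD and Q is the upper normal tail.
- Mild: 0.3 × 0.02275 = 0.7%; 0.3 × 0.06681 = 2.0%.
- Heavy: 0.8 × 0.09121 = 7.3%; 0.8 × 0.15866 = 12.7%.

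**Mean of retained eyes by arm** = [mean − p(mean × Q + SD × φ)]/(1 − pQ), where φ is the normal density at z.
- Mild: better arm −0.3 × 0.005399/0.99318 = −0.0016; other arm (0.050 − 0.3 × 0.016292)/0.97996 = 0.0460. Difference 0.048.
- Heavy: better arm −0.8 × 0.02460/0.92703 = −0.0212; other arm (0.050 − 0.8 × 0.04423)/0.87308 = 0.0167. Difference 0.038.

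**Intact pairs** (simulation of 2,000,000 pairs, same inputs).
- Mild: 0.0489, with 2.6% of pairs lost.
- Heavy: 0.0434, with 17.3% lost.
- True difference 0: 0.000. Each arm's own mean still looks better than it is.

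**Bias against precision.** 400 × 0.8 = 320 and 400 × 0.7 = 280 patients.
- Mild: standard error 0.0056 to 0.0060; bias 0.050 − 0.0489 = 0.0011, and 0.0011/0.0056 = 0.2.
- Heavy: standard error 0.0086 to 0.0092; bias 0.050 − 0.0434 = 0.0066, and 0.0066/0.0086 = 0.77.
- These standard errors remove enhanced pairs on top of an allowance that already includes them. Undoing that in the heavy case multiplies them by √(1 − 0.173) = 0.91, giving 0.0078 to 0.0084 and a ratio of about 0.8.

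**Does a model on the pre-enhancement data help?** Both eyes at Months 1, 3, 6 and 12, between-visit correlation 0.8, enhancement decided at Month 3, Month 12 difference estimated by maximum likelihood with unstructured covariance (400,000 pairs):

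| Case | By arm | Intact pairs | Model |
|---|---|---|---|
| Mild | 0.048 | 0.049 | 0.050 |
| Heavy | 0.041 | 0.045 | 0.050 |

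When the heavy-case decision rests on an unrecorded value, the model gives 0.049.

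**Precision of an enhancement comparison.** The 95% half-width is 1.96 × √[(b + c − (c − b)²)/n], where b and c are the two discordant proportions. Rates are assumed, with 0 to 30% of the lower rate enhanced in both eyes.
- 2% vs 3%: from 1.96 × √[(0.038 − 0.0001)/400] = 1.9 points to 1.96 × √[(0.050 − 0.0001)/280] = 2.6 points.
- 4% vs 7%: from 1.96 × √[(0.086 − 0.0009)/400] = 2.9 points to 1.96 × √[(0.110 − 0.0009)/280] = 3.9 points.

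**The case against.** The strongest reply is that the effect is small and the rule defensible. Keeping only pre-enhancement values is a legitimate way to describe acuity while not retreated. Under a common practice, the heavy-case settings turn true differences of 0.010 and 0.020 into 0.009 and 0.018 in intact pairs. At a true difference of 0, which is the trial's hypothesis, the bias is nil. No margin is stated, so no conclusion can be shown to change, and a 0.050 difference would still be seen as non-zero. Item 9 is also only a general description, and retaining earlier data does not preclude a model that uses them. All of this stands, and it limits the grade of the point. It does not supply the missing comparison of enhancement or a rule for broken pairs. By-visit statistics are the only analysis that the plan describes.

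A reader might infer that the bias could be large or run in either direction because surgeons may enhance the two treatments at different thresholds. The documents do not support this. No passage suggests arm-specific practice, and item 6 places all surgery under the standard of care and the surgeons' usual practice. A reader might also take the 20-30% allowance as an enhancement rate. It covers all drop-out, with enhancement as an unquantified part.

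**Conclusion.** The point holds in a limited form and should be fixed. As written, the plan selects later-visit acuity on an event that follows randomisation and leaves a direct comparison of the treatments unreported. If the treatments truly differ and poor acuity leads to enhancement under one common practice, the later-visit difference is understated. In the illustrations 0.050 logMAR becomes 0.049 to 0.043 in intact pairs, or 0.048 to 0.038 by arm, with enhancement from 0.7% vs 2.0% up to 7.3% vs 12.7%. That is about 0.2 to 0.8 standard errors. The real size is unknown, because the documents give no enhancement rate, SD or margin.

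It would go too far to conclude that the trial will wrongly find equality, that dropping post-enhancement data is itself an error, or that all acuity results are affected. Equal treatments enhanced alike give an unbiased difference, and visits before enhancement are untouched.

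**What to change.** Keep the sentence in item 9 and add two things.

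1. **Enhancement as an outcome.** Pre-specify enhancement (yes/no and date), report it by treatment and compare it within patients with McNemar's test. Include all patients treated in both eyes, use enhancements recorded up to Month 12 or last follow-up, and state the number lost earlier. Do not restrict to patients who completed Month 12 or had an enhancement, because that keeps patients for having the event. For example, with true rates of 4% and 7%, no patient enhanced in both eyes and 30% of non-enhanced patients lost, the denominator falls to 0.11 + 0.7 × 0.89 = 0.733. The rates then become 0.04/0.733 = 5.5% and 0.07/0.733 = 9.5%.
2. **Later-visit acuity.** Compare uncorrected acuity, as logMAR, with a paired repeated-measures mixed model on all pre-enhancement values of both eyes. The fellow eye and the enhanced eye's earlier values then stay in. Keep the by-visit summary, labelled as covering non-retreated eyes only.

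The cost is plan wording, one table and a little more analysis. No new visits or post-enhancement data are needed. Applying the existing rule already requires knowing which eyes were enhanced and when, and first-year enhancement falls under the initial fee, so the site should ordinarily hold the record.

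There are two limits. The enhancement comparison is imprecise (about ±2 to 4 points at the assumed rates), so it can describe a difference but cannot show equality. The model relies on recorded acuity explaining the decision to enhance. No change to when enhancement is performed is proposed.

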**Enrollment Number:**

400

8. **Select the University of Utah department responsible for this research:**

OPHTHALMOLOGY AND VISUAL SCIENCE

9. **Add any additional sites that are part of this performance group**

There are no items to display

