**3. Indicate any vulnerable participant groups (other than children) included:**

None

**If "Other", please specify:****If "None" and no children are involved, answer the following question.****Has the participant selection process overprotected potential subjects who are considered vulnerable so that they are denied opportunities to participate in research?** Yes  No**4. Number of participants to be included and/or enrolled in this entire study, across all study locations:**  
approximately 400**At Utah prior to October 2019:** approximately 400**5. Characteristics of Participants/Inclusion Criteria:**

All subjects who are deemed suitable candidates for laser refractive surgery after routine refractive surgery screening will be considered eligible for participation in this study. Subjects must be at least 21 years of age and not pregnant or nursing (due to fluctuations in visual parameters during pregnancy).

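### Does the target of about 400 participants conflict with the plan's own sample-size inputs?

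*Combined protocol and SAP*

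**What the plan says.** The total appears twice. In the Participants section, item 4, under "Number of participants to be included and/or enrolled in this entire study", the answer is "approximately 400". In the site section, the "Enrollment Number" field also holds 400.

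The basis for size is in Study Information, item 9. It refers to earlier contralateral-eye studies that found significant results by "including in the range of 70-100 patients for each treatment group". It then begins a sentence, "To ensure sufficient patient numbers accounting for 20-30% drop out", which mentions enhancement surgery and ends without a main clause or a number. The same item says: "Standard statistics will be calculated and used to describe the two treatment groups in terms of all study variables". It also says: "Patients withdrawn from the study prior to surgery will not be included in the data analysis and will be replaced in the enrollment group".

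The pairing is set in Study Information, item 6: "Each patient in the study will have a fellow eye enrolled in the other treatment group". That item also says that a patient has the same procedure, LASIK or PRK, in both eyes, and that the patient chooses which. No expected split between the procedures is given, and no rule on whether they are pooled for sizing.

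**The concern.** Item 9 of the form asks for the factors behind the sample size. A reader who takes the two figures given there and applies the drop-out allowance does not arrive at 400. In a fellow-eye design, 70-100 per treatment group means 70-100 patients, because every patient is in both groups. A target several times larger suggests that patients and eyes were confused, or that the pairing was overlooked.

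If 400 meant eyes, the trial would have 200 patients, and the number of completing pairs would be half what the enrolment field implies. If 400 meant patients, several hundred people would be randomised with no stated reason for that number. Either would matter if it led to an underpowered comparison or to a wrong enrolment.

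**Working it through.** **Inputs.** From Study Information, item 9: 70-100 patients per treatment group and 20-30% drop-out. From item 6: one eye per treatment in each patient, so patients equal eyes per group. From Participants, item 4: about 400 participants. Alpha, power, effect size, standard deviation and margin are not stated, so no power formula can be run. The only possible check is inflation for drop-out, n / (1 - d).

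**The plan's figure.** No calculation of 400 is shown, so there is nothing to reproduce directly. The question is which readings lead to it.

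| Reading | Lower end | Upper end |
|---|---|---|
| Pooled, paired (patients) | 70 / 0.8 = 87.5, so 88 | 100 / 0.7 = 142.9, so 143 |
| LASIK and PRK sized separately, equal split, paired (patients) | 140 / 0.8 = 175 | 200 / 0.7 = 285.7, so 286 |
| Four procedure-by-treatment cells (eyes) | 4 × 70 / 0.8 = 350 | 4 × 100 / 0.7 = 571.4, so 572 |

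**Distance from 400.** 400 / 143 = 2.8 and 400 / 286 = 1.4. To reach 400 by drop-out alone, the loss would have to be 1 - 100/400 = 75% (pooled) or 1 - 200/400 = 50% (separate, equal split).

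**The eyes reading.** 4 × 70 / 0.70 = 400, and so does 4 × 100 with no drop-out. The first takes the lowest precedent with the highest loss, the second ignores the loss, and the same formula runs from 350 to 572. The match is weak evidence that eyes were meant.

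**The equal-split assumption.** The second row holds only if half the patients choose each procedure, which the plan does not say. To obtain 88-143 patients in the less-chosen procedure without quotas, the total is that number divided by its share. A total of 400 corresponds to a share of 87.5 / 400 = 22% up to 143 / 400 = 36%. A paired design with separate sizing can therefore give 400 patients. The plan does not say that this was the reasoning, but it does not exclude it.

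**What 400 delivers.** Taken as participants who all have surgery, 400 × 0.7 = 280 to 400 × 0.8 = 320 complete. Against the precedent that is 280 / 100 = 2.8 to 320 / 70 = 4.6 times. If it did mean eyes, 200 patients would leave 140-160 completing, still above 70-100 when pooled.

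These are counts of completers, not of pairs available for analysis. The drop-out figure includes patients who need enhancement surgery, but items 6 and 9 keep their data up to that surgery. Acuity is measured from Day 1 to Month 12 with no single primary time point, so earlier visits can have more pairs.

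**The case for a change.** The case for a change is that the form asks for the basis of the sample size and the answer is incomplete. The sentence breaks off with no sign of redaction, and the word before 400 in the Participants section cannot absorb a gap of 1.4 to 2.8 times. Replacement of patients withdrawn before surgery does not close it either. If 400 counted consented people, the extra loss before surgery would have to be 1 - 286/400 = 28.5%, or 1 - 143/400 = 64% on the pooled reading, and no such rate is given. The two readings of 400 also differ in precision. For a mean eye-to-eye difference, the 95% half-width t(0.975, n-1)/√n is about 0.16-0.17 SD of the paired differences at 160-140 pairs and 0.11-0.12 SD at 320-280. The repair would be a few words.

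Part of this stands. The derivation is missing, the sentence is unfinished, and the pooling basis and the consented-or-operated count are unstated. The rest is weaker. The doubt between patients and eyes has little support, since the field asks for participants and item 9 speaks of patients. The half-widths assume an analysis the plan does not specify and a standard deviation it does not give. The charge of over-enrolment treats the precedent as a ceiling, whereas item 9 reports it as what other studies used and aims for sufficient numbers. The form also describes both treatments as FDA approved and within standard care, so no particular harm from a larger number is shown.

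**Conclusion.** The arithmetic behind the concern is right: the stated inputs give 88-143 patients pooled and 175-286 sized separately with an equal split, against a target of 400. It does not show an error in the plan. The documents never present 400 as the product of those inputs, a target above a cited precedent is consistent with it, and a 22-36% share for the less-chosen procedure would give 400 paired patients.

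What remains is a documentation gap and a clerical slip. A team that enrols 400 participants as written exceeds the precedent and obtains no wrong or less precise result because of this gap. Finishing the sentence would record a reason without altering enrolment, randomisation or analysis.

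This rests on reading the enrolment field literally and on applying drop-out to operated patients. It does not mean that 400, or any of the other numbers, is adequate. The precedent comes from studies that found differences, while this trial's hypothesis is sameness, with no margin or standard deviation stated. That is a separate question, and reconciling these counts would not answer it.
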